12.2 Multiple Comparisons and Control of Type I Error

An IA will be performed after all subjects have reached Week 24 or terminated early. The FA will be performed after all subjects have completed the study at Week 52. As [Figure 2](#) shows, a fixed sequence hierarchical testing strategy will be used to control the Type I error rate across planned analyses (IA/FA) for all efficacy analyses. An O'Brien-Fleming boundary, calculated from a Lan-DeMets alpha spending function, will be used to control the alpha spending for the primary comparison at IA. The details of alpha

spending and the order of testing of the other secondary endpoints are summarized in [Sections 12.3](#) and [Section 12.4](#).

Figure 2: Two-sided Alpha Available for Spending in the Fixed Sequence Hierarchical Testing Procedure

12.3 Interim Analysis

The study will have one unblinded (partial) interim analysis (IA). An unblinded statistical team from Everest will perform the analyses. The IA will be based on the ITT analysis set.

To facilitate the IA, certain sponsor representatives and designees may be unblinded to individual treatment assignments prior to and during the IA (including the unblinded clinical research organization (CRO) biostatistician and external groups for bioanalytical, PK, and PK/PD analyses). Details are provided in the study unblinding plan. The blinded Sponsor and CRO study team members will be unblinded solely to the group analysis results (but not individual subject results) at the conclusion of the IA.

The IA will be performed after all subjects have reached Week 24 or terminated early. The IA will include summaries of disposition, baseline demographics and disease characteristics, safety analysis (summary of adverse events, change from baseline for laboratory [excluding specialty hematology], vital sign and 12-lead ECG parameters), as well as analyses of the efficacy endpoints.

At the IA, all the efficacy endpoints will be tested in a hierarchical order, at the highest tolerated dose of IMR-687 vs placebo. If all the efficacy comparisons are successful, testing of the IMR-687 pooled dose vs. placebo, and of lower dose vs. placebo will be performed. If the first comparison fails (i.e. the null hypothesis is not rejected), the statistical analysis and the p-values from all remaining comparisons will

not be reported at the interim analysis. The hierarchical order of testing of primary, key secondary and other secondary endpoints is:

1. Annualized rate of VOCs
2. Time to first VOC
3. HbF responder rate at Week 24
4. Proportion of VOC-free subjects
5. Annualized rate of VOC-related hospitalization
6. Annualized rate of days hospitalized for VOC-related hospitalizations
7. Time to second VOC
8. Change from baseline in key biomarkers of RBC hemolysis (indirect bilirubin and % reticulocytes) at Week 24
9. Change from baseline in HbF (%) and F-cells (%) at Week 24
10. Hb responder rates at Week 24
11. Change from baseline in total Hb (g/dL) at Week 24
12. Change from baseline in other biomarkers of RBC hemolysis (absolute reticulocytes and lactate dehydrogenase [LDH]) at Week 24
13. Change from baseline in biomarkers of adhesion such as soluble E-selectin (E-sel), P-selectin (P-sel), intercellular adhesion molecule 1 (ICAM-1), and vascular cell adhesion molecule 1 (VCAM-1) at Week 24
14. Change from baseline in biomarkers of inflammation such as high-sensitivity C-reactive protein (hsCRP) and myeloperoxidase (MPO) at Week 24
15. Change from baseline in biomarkers of cardiac stress such as N-terminal prohormone of brain natriuretic peptide (NT-proBNP) at Week 24
16. Change from baseline in RBC indices, such as mean corpuscular volume (MCV) at Week 24
17. Change from baseline in each measured subdomain of ASCQ-Me questionnaire at Week 24
18. Change from baseline in total preference score and individual domain scores of PROPr questionnaire at Week 24
19. Change from baseline in overall score of the Sickle Cell Self-Efficacy Scale (SCSES) at Week 24

The primary efficacy endpoint (annualized rate of VOCs) will be tested using a stratified Wilcoxon rank-sum test. The annualized rate of VOCs will be based on the data collected once all subjects have reached Week 24. Based on the proportion of information available at the IA (24 weeks at IA/52 weeks at FA = 0.4615), the alpha spending and O'Brien-Fleming boundaries as implemented by a Lan-DeMets alpha spending function will be as shown in [Table 5](#) below. The lower bound of O'Brien-Fleming boundary will be used as the critical value to test the primary endpoint at the highest tolerated IMR-687 dose. If the p-value from the primary comparison is equal or below the critical value at the IA, the success of the primary efficacy analysis can be claimed. If not, the comparison will be re-done at the FA, when the information from the whole study is available, using a propagated alpha (also shown in [Table 5](#)).

Table 5 Alpha Spending Summary

| Analysis | One-sided Nominal p-Value (Lower Bound of O'Brien-Fleming Boundary) | Two-sided Nominal p-Value | Lower Bound Alpha Spending |
|------------------|--|---------------------------|----------------------------|
| Interim Analysis | 0.0010 | 0.0020 | 0.001 |
| Final Analysis | 0.0247 | 0.0494 | 0.024 |
| Total | | | 0.025 |

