Initially, subjects will be randomly assigned in a 2:1 ratio to receive either IMR-687 lower dose or placebo. Prior to the introduction of IMR-687 higher dose, the Data Monitoring Committee (DMC) will review safety data for at least 5 subjects who received IMR-687. If the DMC recommends inclusion of the higher dose, randomization will then proceed in a 1:2:1 ratio (IMR-687 lower dose, IMR-687 higher dose, or placebo). During study conduct under Protocol Version 3.0, the DMC approved opening of enrollment to the higher dose IMR-687 group, enrollment to the higher dose went into effect on 12 March 2021.

[figure not shown]
Subjects may or may not be concomitantly receiving a stable dose of hydroxyurea (HU) according to the subject's established treatment plan. Randomization will be stratified by use of HU (yes vs. no) and by region (North America/Europe vs. Africa/Middle East).

Subjects will be directed to take study drug (either IMR-687 or placebo) with food, but if a subject does not do so, it will not be considered a protocol deviation.

An interim analysis (IA) will be conducted when all subjects have completed study assessments (including VOC incidence) at Week 24 or terminated the study early. The IA will be a partial unblinding event with corresponding alpha spending strategies to manage Type 1 error.

A final analysis (FA) will be conducted at study completion (i.e., when all subjects have reached Week 56 or terminated early), following database lock and unblinding. Alpha available at the final analysis will be propagated based on the alpha spent from the IA.

Figure 1: Overview of Study Design and Dose Groups

Abbreviation: DMC = data monitoring committee.

* Prior to the introduction of IMR-687 higher dose, the DMC will review safety data for at least 5 subjects who received IMR-687. If the DMC recommends inclusion of the higher dose, randomization across 3 dose groups will then proceed as shown.

During study conduct under Protocol Version 3.0, the DMC approved the opening of enrollment in the higher dose IMR-687 group, which went into effect on 12 March 2021.

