8.1 Sample Size and Power Considerations

8.1.1 Sample Size Determination

The sample size of this study was originally determined based on HbF responder rate as the primary endpoint:

Assuming a 5% HbF response rate for placebo, the study having approximately 31 placebo and 49 higher dose subjects would have > 85% power to detect a targeted difference of 30%, using a Chi-square test for comparison of proportions (with continuity-correction) and a two-sided alpha of 0.050. The assumed responder rate for placebo (5%) and highest tolerated dose subjects (>35%) includes the dropout subjects (regarded as are non-responders at Week 24).

Based on FDA feedback a new primary endpoint was adopted with a corresponding change in statistical methodology as specified in Section 8.1.2 below.

As of completion of this SAP, enrollment was completed in the ongoing study, with a total of 115 subjects randomized between August 2020 and August 2021. Out of the 115 subjects, the first 17 subjects were randomized in a 2:1 ratio to Lower Dose: Placebo, and the remaining 98 subjects proceeded with randomization in a 1:2:1 ratio for Lower Dose: Higher Dose: Placebo.

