12.0 Overview of Planned Analyses

This section summarizes the planned analyses for efficacy, PD, PK and safety for the interim analysis (IA) and final analysis (FA). The statistical analyses, which will be performed on locked and cleaned data extracts, will include all data through protocol-specified analysis time points. The data cut-off for the IA are specified below. The DMC may recommend the discontinuation of a dose arm, due to safety, which will inform the highest tolerated dose. Selected personnel involved in the analysis and review of unblinded data for the IA will abstain from attending study conduct and operational meetings after the data has been unblinded for any reason. Detailed statistical methods are defined in [Section 13.0](#).

An IA will be performed after all subjects have reached Week 24 or terminated early. The FA will be performed after all subjects have completed the study. The critical significance levels for the IA and FA to maintain an overall two-sided type I error rate of 5% will be based on an O'Brien-Fleming boundary, calculated from a Lan-DeMets alpha spending function, based on the number of highest tolerated dose and placebo subjects used in the primary efficacy analysis in the ITT analysis set.

A summary of planned analysis for IA/FA are summarized in [Table 4](#) below.

Table 4 Planned Analyses for IA and FA

| | IA | FA |
|--|--|--|
| Disposition, Baseline and Disease Characteristics | Yes | Yes |
| Exposure | Yes | Yes |
| Concomitant and Prior Medications | | Yes |
| Primary Efficacy: Annualized Rate of VOCs | Yes, with Alpha spending - fixed sequence design [a] | Yes, with propagated Alpha from IA [a] |
| Key Secondary Efficacy: Time to first VOC and HbF Responder rate at Week 24 | Yes [b] | Yes [b] |
| Other Secondary Efficacy: Biomarkers and Specialty Hematology parameters | | Yes |
| Other Secondary Efficacy (Annualized rate of VOC-related hospitalizations, etc.) | | Yes |
| Other Secondary Efficacy: PROs (ASCQ-Me, PROPr, SCSES) | | Yes |
| Exploratory Efficacy | | Yes |
| Subgroup Analysis | | Yes |
| Safety (AEs, Laboratory, Vital Signs, ECGs, etc.) | Yes, selected outputs only | Yes |
| PK | Yes, selected outputs for plasma concentration only | Yes |

[a] Two-sided alpha spending at IA for primary efficacy analysis is 0.002. Propagated Alpha of 0.0494 is to be spent at FA.

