TEAEs leading to dose reduction will be identified by action taken with study treatment being recorded as “Dose Reduced” on the Adverse events CRF.

Overall Summary

An overall summary of TEAEs will be presented by treatment group for the safety analysis set. The number and percentage of subjects reporting any of the following categories will be provided:

- Any pre-treatment adverse event
- Any TEAE
- Grade 3 or higher TEAEs
- Treatment-related TEAEs
- Treatment-related grade 3 or higher TEAEs
- Treatment-related grade 2 or higher TEAEs
- SAEs
- Treatment-related SAEs
- Treatment-related grade 3 or higher SAEs
- TEAEs leading to death

- TEAEs leading to discontinuation of study drug
- Treatment-related TEAEs leading to discontinuation of study drug
- TEAEs leading to study discontinuation
- Treatment-related TEAEs leading to study discontinuation
- TEAEs leading to dose reduction
- Treatment-related TEAEs leading to dose reduction

The following AE summaries will be by treatment group, SOC and PT for the safety analysis set. SOCs will be sorted alphabetically and PTs will be sorted by descending frequency in the pooled IMR-687 treatment group column, and then alphabetically for ties.

- The number and percentage of subjects with any TEAE. The AE count will be for subjects not events, and subjects are only counted once within each SOC or PT
- The number and percentage of subjects with Grade 3 or higher TEAEs
- The number and percentage of subjects with Treatment-related TEAEs. Subjects with multiple events within a particular SOC or PT will be counted under the category of their most drug-related event within that SOC or PT (related or not related). AEs will be considered related to study drug if they are reported as certain/related, probably/likely related, or possibly related.
- The number and percentage of subjects with Treatment-related TEAEs
- The number and percentage of subjects with Treatment-related Grade 3 or higher TEAEs
- The number and percentage of subjects with Treatment-related Grade 2 or higher TEAEs
- The number and percentage of subjects with SAEs
- The number and percentage of subjects with Treatment-related SAEs
- The number and percentage of subjects with Treatment-related Grade 3 or higher SAEs
- The number and percentage of subjects with TEAEs leading to death
- The number and percentage of subjects with TEAEs leading to discontinuation of study drug

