Appendix 4 Data Handling Rules

| Category | Description | Data Handling Rule |
|--|---|---|
| 1. Age (years) | Age (years) | Age is collected from Demographics CRF page. |
| 2. First Dose Date/Time of Study Drug | date/time of first dose of study drug | The date and time (24 hr. clock) of the first dose of study drug will be taken from the Study Drug Administration CRF. |
| 3. Last Dose Date of Study Drug | date of last dose of study drug | 
The date of the last dose of study drug will be the Date of last dose from the End of Treatment CRF.
 
If it is missing for the IA, and DMC analyses, use the data cutoff date.
 
If it is missing at the database lock, the date of the last dose of study drug will be imputed as the later of last visit date, last dispensing date (from Drug Accountability CRF), date of Completion/Discontinuation, and death date.
 |
| 4. Last Visit Date | Date of Last Visit | Date of last visit according to the Clinic Visit and Telephone CRF. |
| 5. Last Study Participation Date (STDM variable, typically named RFPENDTC) | Last Study Participation Date (STDM variable, RFPENDTC), where SDTM denotes Study Data Tabulation Model | Last study participation date is defined as last known date of contact which would be the later of the following dates: last visit date, date of the last dose, date of Completion/Discontinuation, date of clinical study follow-up, or death date. |
| 6. Study Day Definitions | Study Day for an assessment/event which occurred on or after the start of study drug | Study Day = Date of assessment/event – date of the first dose of study drug + 1. |
| | Study Day for an assessment/event which occurred on a day prior to the first dose of study drug in the study | Study Day = date of assessment/event – first dose date of study drug in the study. |
| | Study Day of Randomization | Study Day of Randomization = date of randomization – date of the first dose of study drug in the study + 1. Study Day is 1 if baseline day is on the day of randomization. |
| | First Dose Day | First Dose Day in the study is defined as the study day of the first dose of study drug in the study (Study Day 1). |
| | Last Dose Day | Last Dose Day in the study is defined as the study day of the last dose of study drug in the study. |
| 7. Duration of an event | The duration of any event | The duration of an event is defined as (stop date – start date + 1). |

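### At the interim analysis the higher-dose arm has been watched for less time than placebo or lower dose, so crude TEAE and SAE percentages modestly understate its share of events that accrue over time

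*SAP*

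**What the plan says.** Randomisation was in two stages. SAP 8.1.1 reports enrolment complete, "with a total of 115 subjects randomized between August 2020 and August 2021". In the first stage, "the first 17 subjects were randomized in a 2:1 ratio to Lower Dose: Placebo". The higher dose was available only in the second stage, when "the remaining 98 subjects proceeded with randomization in a 1:2:1 ratio". SAP 8.0 dates the change: "enrollment to the higher dose went into effect on 12 March 2021". SAP 13.0 pools lower dose and placebo across the two stages with no adjustment.

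The interim analysis (SAP 12.3) takes place once every subject has reached Week 24 or left early. It includes a "safety analysis (summary of adverse events, change from baseline for laboratory [excluding specialty hematology], vital sign and 12-lead ECG parameters"). For subjects with no recorded last dose, Appendix 4 (item 3) says: "If it is missing for the IA, and DMC analyses, use the data cutoff date". SAP 13.5.2.1 applies the same rule to the VOC rate and expects it to be needed for only some interim subjects. SAP 10.4 counts TEAEs up to 30 days after the last dose and sets no common time limit.

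The adverse-event tables in SAP 13.5.8.1 share one metric: "The number and percentage of subjects with any TEAE. The AE count will be for subjects not events". Exposure duration is summarised by arm (SAP 13.3) and is an interim output (SAP Table 4), but it is never the denominator for an adverse-event rate.

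**The concern.** A crude percentage of subjects with an event rises with the time each subject is watched. The longest-followed subjects at the interim look are the first 17, and none could be on the higher dose. If the arms had identical risk, the higher dose would still show the lowest percentage for any event that goes on accruing. The primary efficacy endpoint is annualised for time on drug; the harms are not.

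At stake is the interim safety picture of the newest and highest dose. After the interim analysis the blinded sponsor and CRO teams see group-level results (SAP 12.3), and the DMC may receive group-level summaries (SAP 12.5). If the efficacy boundary is crossed, SAP 13.5.2.2 allows unblinding and an offer of active drug to placebo subjects, so this could become the last intact placebo-controlled safety comparison.

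**Working it through.** **Arm sizes (the plan's own figure).** From SAP 8.1.1:

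- Lower dose: 17 × 2/3 + 98 × 1/4 = 11.33 + 24.5 = 35.8
- Higher dose: 98 × 1/2 = 49
- Placebo: 17 × 1/3 + 98 × 1/4 = 5.67 + 24.5 = 30.2

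SAP 8.1.2 projects 35, 49 and 31, so these agree. The share from the first stage is about 11/35 = 31% for lower dose, 6/31 = 19% for placebo and 0/49 for higher dose.

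**Adverse-event window.** The SAP gives no follow-up by arm, so it must be modelled. Assumptions:

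- even accrual within each stage, from 15 August 2020 to 15 August 2021 (the SAP gives months only);
- cut-off 168 days after the last subject enters, i.e. 30 January 2022;
- no dropout;
- window capped at 364 + 30 = 394 days.

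Second stage: entry runs over the 156 days from 12 March to 15 August 2021, so follow-up runs evenly from 168 to 324 days. The mean is 168 + 156/2 = 246 days = 35.1 weeks.

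First stage: entry runs over 209 days, so uncapped follow-up runs from 324 to 533 days. A share (394 − 324)/209 = 0.335 falls below the cap, with mean 359 days; the rest sit at 394. The mean is 394 − 0.335 × 35 = 382.3 days = 54.6 weeks.

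| Arm | Mean window (weeks) |
|---|---|
| Higher dose | 35.1 |
| Placebo | (5.67 × 54.6 + 24.5 × 35.1)/30.17 = 38.8 |
| Lower dose | (11.33 × 54.6 + 24.5 × 35.1)/35.83 = 41.3 |

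Moving the first and last entry to either end of August, and capping at 364 or 394 days, gives 34-36, 37-40 and 39-42 weeks. The order never changes.

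**Effect on crude percentages.** Give every arm the same constant hazard, here 0.7 per year. The expected percentage is the average of 1 − exp(−0.7t/365.25) over each subject's follow-up t in days: 37.4% in the second stage and 51.9% in the first.

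- Higher dose: 37.4%
- Placebo: (5.67 × 51.9 + 24.5 × 37.4)/30.17 = 40.1%
- Lower dose: (11.33 × 51.9 + 24.5 × 37.4)/35.83 = 42.0%

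The gaps are 2.7 and 4.6 points, with no true difference. Over 24-week risks from 10% to 70% and the August date range, higher dose reads 1.1-3.2 points below placebo and 1.8-5.2 below lower dose.

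**With dropout.** Using the 25% of SAP Table 1, spread at a constant rate over 52 weeks with a 30-day tail after dropout, the 0.7-per-year example gives 35.0%, 37.2% and 38.7%. The gaps shrink to 2.2 and 3.7 points.

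**Against sampling error.** Higher dose versus placebo: √(0.401 × 0.599/31 + 0.374 × 0.626/49) = 0.11, or about 11 points. One placebo subject is 1/31 = 3.2 points.

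**The case against.** The strongest reply is that this is a small, temporary imbalance in descriptive tables. The gap against placebo is less than one placebo subject in the worked example and well inside sampling error. Exposure duration is already an interim output, so an attentive reader can see the unequal follow-up. The known drug-related nausea began 30 to 120 minutes after dosing (Protocol 4.2.3.1), so follow-up length hardly matters for it, and by-visit changes in laboratory values, vital signs and ECG compare the arms at common visits. All of that stands and limits the size of the point. It does not remove the bias, which always favours the same arm.

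A second reply is that interim data may stop at Week 24. SAP 12.0 limits the analyses to data up to the time points that the protocol specifies, and SAP 12.3 takes the information fraction as 24/52. Truncation at Week 24 would close the gap. But SAP 13.5.2.1 and Appendix 4 end exposure at the cut-off date, so the SAP is ambiguous and should say which applies.

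Two stronger readings are tempting. One is that DMC reviews suffer the same bias and so distort the highest tolerated dose, since "The DMC may recommend the discontinuation of a dose arm, due to safety, which will inform the highest tolerated dose". The documents do not support this. They list the data the DMC may see but leave its procedures to a charter that is not among them, so the metric is unknown. The DMC recommends rather than decides, and Protocol 8.7 sets no event-frequency stopping rule. The SAP is dated 1 March 2022; a subject entered as late as 31 August 2021 had completed 168 days by 15 February 2022, so a remedy for reviews before Week 24 would reach nobody.

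The other is that interim counts of potentially clinically significant values are understated too. SAP 12.3 does not name those tables, and SAP Table 4 promises only selected safety outputs.

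**Conclusion.** The point holds for TEAE and SAE percentages at the interim analysis, for events that accrue over time. If follow-up runs to the cut-off, the higher-dose percentage is understated by about 1-3 points against placebo and 2-5 against lower dose. This rests on even accrual, equal constant hazards and no dropout; with dropout it is smaller. It is less than sampling error, and it would vanish if the SAP meant to truncate at Day 168. At the final analysis every arm has the same planned window, so only differential dropout could produce a gap. A reader should not conclude that the higher dose will look materially safer than it is. The conclusion is that a known one-directional error sits in the interim tables and can be removed cheaply.

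**What to change.** In SAP 12.3 and 13.5.8.1, for the interim analysis and any later DMC output built from the same tables:

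1. State whether interim adverse-event data run to the cut-off or stop at Week 24.
2. Tabulate TEAEs and SAEs with onset on or before Day 168 for all subjects. The interim trigger makes this a window that all arms share.
3. Beside the crude percentages, give exposure-adjusted incidence: subjects with an event per 100 subject-years at risk.
4. Do the same for counts of potentially clinically significant values only if those tables are among the selected interim outputs.

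Under equal constant hazards, either the Day 168 window or the adjusted rate restores an expected ratio of 1.00 between arms. They complement each other: the adjusted rate also allows for early withdrawal, while the Day 168 table is safer for early-onset events, where dividing by later event-free time would make the shorter-followed arm look worse.

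The cost is SAP wording and a few extra table columns from data already held. The Day 168 tables omit later events, which stay in the all-data tables.

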13.5.2.1 Derivation of Annualized Rate of VOCs

As described in Protocol Inclusion Criterion 3, a VOC is defined as a documented episode of acute painful crisis (for which there was not an explanation other than VOC) that involves moderate to severe pain lasting for at least 2 hours and at least one of the following:

- Use of escalated analgesia (including healthcare professional-instructed use of an analgesic prescription)
- A hospital, emergency department, or clinic visit and/or healthcare telephone consultation at the time of occurrence
- Diagnosis of acute chest syndrome (ACS) (defined as an acute illness characterized by fever and/or respiratory symptoms, accompanied by a new pulmonary infiltrate on a chest X-ray), hepatic sequestration, or splenic sequestration, or priapism (in males)

VOCs collected during the study are assumed to meet these criteria as well.

VOC information, including start and end date/time, primary setting for treatment (hospitalization/ emergency department, etc.), and treatments are collected on the "VOC" CRF page.

Annualized rate of VOCs is calculated as Total number of VOCs / ([Date of last dose of study drug– date of first dose of study drug + 1]/365.25).

Date of last dose of study drug is collected from the "End of Treatment" CRF page. If that date is not available (which is expected for some of the subjects in the IA), the data cut-off date will be used.

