Appendix 6 SAS Codes for Statistical Analysis

| Test | Template SAS Code for Modeling (SAS Version 9.4) |
|--|--|
| Determination of lower O'Brien-Fleming stopping boundary for the primary efficacy endpoint at the interim analysis | Proc Seqdesign errspend plots=all boundaryscale=pvalue; PrimaryEfficacy: design alpha = 0.05 beta = 0.20 alt = twosided /* two-sided test*/ nstages = 2 method (reject)= errfuncobf /* O'Brien-Fleming as implemented by Lan-DeMets */ info = cum(24 52) /* information proportion are based on 24 wks out of 52 wks*/; run; |
| Primary Analysis: Stratified Wilcoxon rank-sum test | proc npar1way data=ITT; Title 'Primary Endpoint – Comparison of Annualized VOC Rates'; Title2 'Intent To Treat Population'; class TRT; var ARVOC; strata <stratification factors: REGION HU >; run; |
| Negative binomial regression | proc genmod data=ITT; Title 'Sensitivity Analysis for Primary Endpoint – Negative Binomial Regression'; class TRT <stratification factors: REGION HU >; /*TRT is treatment group; model Y = TRT <stratification factors: REGION HU> / dist = negbin link = log offset = LTIME; /*Y is the count of VOC, LTIME is the log of exposure time in years; lsmeans TRT / cl diff exp; |
| Time to Event Analysis | proc lifetest data=ITT plots=(survival(nocensor atrisk cb)); Title 'Secondary Endpoint – Time to Event Analysis Time to first VOC'; time TIME*VOC(0); Strat TRT; run; |
| Mixed model repeated measures (MMRM) | proc mixed data=ITT; class SUBJECT TRT VISIT HU REGION; model CFB = TRT VISIT TRT*VISIT BASELINE HU REGION; /*CFB=change from baseline; repeated VISIT/ TYPE = UN ddfm=kr sub=SUBJECT; /*Type=CS and then Type AR(1) will be used if UN does not work*/ lsmeans TRT*VISIT/cl diff alpha=0.05; lsmeans TRT/cl diff alpha=0.05; run; |
| Multiple Imputation for the annualized rate of VOCs | proc mi; class TRT REGION HU ; fcs reg(AVOC = TRT REGION HU VOC_O DUR); /*AVOC= annualized VOC rate; VOC_O =Number of observed VOCs; DUR = Duration in the study. run; |

| Test | Template SAS Code for Modeling (SAS Version 9.4) |
|--|---|
| with FCS Method | |
| Negative binomial regression based on Multiple Imputed dataset | <pre>proc genmod data=MIDATA; by _imputation_; class TRT REGION HU ; /*TRT is treatment group; model Y = TRT REGION HU / dist = negbin link = log offset = LTIME; *Y is the count of VOC, LTIME is the log of exposure time in years; lsmeans TRT / cl diff exp; run;</pre> |

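### SAP 12.3 shows interim group results to the sponsor and CRO team that Protocol 10.2 keeps blinded until study conclusion; as a minor matter, the interim information basis, data cut and final alpha are stated inconsistently

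*SAP*

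**What the plan says.** **Access to interim results.** Protocol 10.2 (Blinding) has the blinded sponsor and CRO team learn the analysis results at the conclusion of the study, with database lock as its example. Protocol 10.3 unblinds only certain representatives and designees for the interim work. SAP 12.3 (Interim Analysis) also allows certain people to be unblinded to individual assignments. It then adds that the blinded sponsor and CRO team will see the group results, though not individual ones, when the IA concludes. It attaches no condition about the boundary. SAP 6.0 says the SAP prevails where it differs from the protocol. SAP 12.0 keeps selected personnel who handle unblinded IA data out of operational meetings. SAP 12.5 already lists group-level IA reports among the material for the DMC.

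**Information basis and levels.** SAP 12.0 derives the levels from a Lan-DeMets O'Brien-Fleming function "based on the number of highest tolerated dose and placebo subjects used in the primary efficacy analysis in the ITT analysis set". SAP 12.3 instead writes "Based on the proportion of information available at the IA (24 weeks at IA/52 weeks at FA = 0.4615"), and the template code in Appendix 6 carries the comment "information proportion are based on 24 wks out of 52 wks". SAP 12.0, Table 4 footnote [a], fixes the levels: "Two-sided alpha spending at IA for primary efficacy analysis is 0.002. Propagated Alpha of 0.0494 is to be spent at FA". Table 5 gives the same pair. SAP 13.5.7 (Multiplicity Adjustment) says endpoints are tested at 0.05.

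**Data cut.** SAP 12.0 promises that "The data cut-off for the IA are specified below", but only the trigger follows. SAP 8.0 places the IA "when all subjects have completed study assessments (including VOC incidence) at Week 24 or terminated the study early". SAP 13.5.2.1, for a missing last-dose date, says "If that date is not available (which is expected for some of the subjects in the IA), the data cut-off date will be used". Appendix 4 agrees: "If it is missing for the IA, and DMC analyses, use the data cutoff date".

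**The concern.** The main issue is conduct. A vaso-occlusive crisis (VOC) in this trial depends on clinical judgement (moderate to severe pain, escalated analgesia, a contact with care), and SAP 13.5.2.1 assumes that recorded events meet the definition. Before lock the sponsor still classifies important deviations (SAP 13.2) and defines per-protocol exclusions (SAP 11.6), and SAP 6.0 foresees SAP updates up to database lock. A team that knows the group result while doing these things is a recognised source of operational bias. The provision also undercuts the separation of personnel in SAP 12.0.

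The lesser issue is that the SAP gives two incompatible descriptions of interim information, leaves the IA data cut open to two readings, and states a third alpha in 13.5.7. Two programmers could compute different interim rates, and the final test could be read against 0.05 or 0.0494.

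**Working it through.** **1. Access rules side by side.**

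| Place | Who | Sees what | When |
|---|---|---|---|
| Protocol 10.2 | Blinded sponsor and CRO team | Analysis results | Conclusion of the study |
| Protocol 10.3 | Certain representatives and designees | Treatment assignments | Before and during the IA |
| SAP 12.3 | Blinded sponsor and CRO team | Group results | Conclusion of the IA |
| SAP 13.5.2.2 | Study may be unblinded | - | Only if the boundary is crossed at the IA |

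Rows 1 and 3 name the same people and different times. SAP 6.0 resolves the conflict in favour of row 3. Row 4 is conditional, so it does not explain row 3.

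**2. Follow-up still to come.** Inputs: 115 randomized August 2020 to August 2021, the first 17 at 2:1 and the next 98 at 1:2:1 (SAP 8.1.1); higher dose open from 12 March 2021 (SAP 8.0); treatment 52 weeks. This gives 98 × 2/4 = 49 higher dose and 17/3 + 98/4 = 30.2 placebo. Assumptions: even accrual within each phase, no dropout. Take accrual from 15 August 2020 to 15 August 2021 and the SAP date, 1 March 2022. Second-phase subjects then have 28.3 to 50.6 weeks, mean 39.4, or 39.4/52 = 0.758; first-phase placebo have 0.999. The combined fraction is (73.5 × 0.758 + 5.67 × 0.999)/79.2 = 0.775, so 22% remains. Over the possible August dates the range is 21-25%. This is an upper limit, because an IA run under this SAP reports after that date.

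**3. Reproducing Table 5.** Per side, α(t) = 2[1 − Φ(z₀.₉₈₇₅/√t)] with t = 24/52 = 0.4615. Here 2.2414/0.6794 = 3.299, so α = 0.00097, which is the stated 0.0010. Two-sided this is 0.0019; the stated 0.0020 is twice the rounded one-sided figure. Solving the bivariate normal with correlation √t for total error 0.05 gives a final level of 0.04935, the stated 0.0494.

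**4. Does either basis describe the data?**
- *Subject numbers (SAP 12.0).* Enrolment is complete and the ITT set is used at both looks, so the fraction is 1.0 and the function would spend the whole 0.05 at the IA.
- *24/52.* As person-time, this fits only if every subject is cut at Week 24. SAP 8.0 allows that reading, as does the SAP 12.0 statement that analyses use data through protocol-specified time points. SAP 12.3 (data collected once all have reached Week 24), 13.5.2.1 and Appendix 4 point to the cut-off date.
- *Cut-off date.* With the mid-August dates and a cut 24 weeks after the last entry, second-phase subjects average (24.0 + 46.3)/2 = 35.1 weeks, or 0.676; first-phase placebo have 0.989. Combined: (73.5 × 0.676 + 5.67 × 0.989)/79.2 = 0.70. Over the possible August dates it is 0.68-0.72. With the SAP's 25% dropout at a constant hazard it is 0.71-0.74.

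**5. Total two-sided error.** 1 − P(|Z₁| < c₁, |Z₂| < c₂), correlation √t, c₁ = 3.09 for the IA at 0.002.

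| Fraction | Final level 0.0494 | Final level 0.05 |
|---|---|---|
| 0.4615 | 0.0501 | 0.0507 |
| 0.70 | 0.0495 | 0.0501 |
| 0.80 | 0.0494 | 0.0500 |

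**The case against.** **On access.** SAP 8.0 calls the IA a partial unblinding event, so group-level disclosure may be deliberate. Individual allocations, sites and subjects stay blinded, enrolment is complete, and the per-protocol set serves only sensitivity analyses. If the first comparison fails, SAP 12.3 withholds the remaining comparisons, and its wording leaves some doubt about what is reported for the primary. Both documents defer details to an unblinding plan that is not available here. All this limits the risk. It does not reconcile the two texts, and withholding the later results would itself tell the team that the primary had failed.

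A reader might infer that the trial is effectively unblinded at the IA. The documents do not support that: only group results are released.

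**On alpha.** SAP 12.2 refers to 12.3 and 12.4 for the alpha details, the levels are fixed numerically in two places, and the phrase in 12.0 might merely name the comparison population. So this part has almost no operative effect, and that stands. Two stronger readings fail. One is that the interim boundary inflates type I error; step 5 shows otherwise for the stated pair. The other is that the SAP allows the interim level to be re-derived upward; no provision does so. Conversely, one cannot say that all stated levels agree, because 13.5.7 differs.

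**Conclusion.** The access conflict is direct and should be corrected before interim results are released. SAP 12.3 releases to the blinded team what Protocol 10.2 withholds, and the precedence clause makes the weaker rule operative. The potential for bias is real but limited: at most 21-25% of the relevant person-time was outstanding at the SAP date, under even accrual and no dropout, and individual assignments remain concealed.

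The information-basis point is minor. The subject-number wording cannot yield 0.4615, and 24/52 describes the data only under a Week 24 cut. The person-time fraction at a cut-off date (0.68-0.72) depends on assumed accrual, and information for a rank test need not equal person-time. The conclusion does not depend on that choice: with 0.002 and 0.0494 kept, total error stays within 0.0494-0.0501 for fractions 0.46-0.80. The only alpha wording that matters numerically is in 13.5.7. Used at the final analysis, 0.05 gives total error 0.0507 at 0.4615, a small excess that is easily removed.

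**What to change.** **Access (SAP 12.3).** Align with Protocol 10.2: interim group results go to the DMC, as SAP 12.5 already provides, and to the unblinded group named in the unblinding plan. The blinded sponsor and CRO team sees results only at study conclusion, unless the boundary is crossed and the study is unblinded under SAP 13.5.2.2. Carry the same line into the unblinding plan. Restricting release to the DMC and a named group is one way to meet Protocol 10.2, which does not itself prescribe it. The cost is that the blinded team waits for the final analysis.

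**Alpha and data cut.** Delete the subject-number basis in SAP 12.0. In SAP 13.5.2.1, state one rule for where interim VOC counts and exposure stop (Week 24 or a defined cut-off date), and match it in SAP 8.0 and Appendix 4. State that 0.002 and 0.0494 are fixed whatever fraction is realised. The interim level should not be revised upward: even with a last entry on 31 August 2021, all subjects had passed 168 days by 15 February 2022, before the SAP date. In SAP 13.5.7, replace 0.05 with 0.0494 for the final analysis. This costs a few sentences and needs no new boundary calculation; the interim test stays strict.
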